8.3.3.3. Biomarkers

8.3.3.3.1. FeNO

Actual values, change from baseline values, and percent change from baseline values will be summarized by visit. LS means, SEs, and corresponding 95% CIs for each treatment group and differences in LS means, SEs, and corresponding 95% CIs for each GB001 group versus placebo will be constructed from ANCOVA models without MI for both change and percent change from baseline to Week 24. The models will include covariates for treatment group and baseline FeNO.

FeNO data will also be presented in a by-subject data listing.

8.3.3.3.2. Sputum Eosinophils and Neutrophils

As sputum eosinophils and neutrophils are known to follow a log-normal distribution, analyses will be based on a log10-transformed scale, with results back-transformed to obtain the following statistics:

- Baseline geometric means and % coefficients of variation (CV), and corresponding 95% CIs by treatment group
- Week 24 geometric means, % CV, and corresponding 95% CIs by treatment group
- Within-treatment group geometric mean ratios (GMRs) for LS means for change from baseline to Week 24, using an ANCOVA model adjusting for log of baseline value, SEs, and corresponding 95% CIs
- Percent reduction in the above within-treatment group GMRs for LS means for change from baseline to Week 24 for each GB001 group versus placebo, corresponding 95% CIs, and p-values from the ANCOVA model

Sputum eosinophils and neutrophils will also be presented in a by-subject data listing.

8.3.3.4. PK Concentrations

GB001 plasma concentrations will be summarized by visit/timepoint using the following descriptive statistics: number of subjects with non-missing data, arithmetic mean, SD, arithmetic % CV, geometric mean, geometric % CV, median, minimum, and maximum.

For calculation of mean concentrations, all below limit of quantification (BLQ) values will be set to zero. If the number of values that are BLQ at a nominal timepoint exceed 50% of the observations collected at that nominal timepoint, summary statistics for the timepoint will not be calculated. If the mean concentration value is less than the lower limit of quantification (LLOQ) value, then the mean, median, minimum, and maximum concentration values will be set to BLQ.

PK concentrations will also be presented in a by-subject data listing.

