Subjects will be provided with an eDiary which is programmed to alert the subject of potential asthma worsening:

1. On 2 consecutive days, AM PEF \leq 75% of mean AM PEF measured over the last 7 days of the Run-in period
2. Increase in rescue medication use of \geq 6 puffs/day (last 24 hours) on 2 consecutive days compared to mean use over the last 7 days of the Run-in period
3. Nighttime awakening due to asthma symptoms requiring rescue medication for at least 2 of 3 successive nights
4. An asthma symptom score of 4 for at least 2 of 3 successive days.

Upon receiving an alert, the subject should contact the site staff as soon as practical to assess the subject's asthma status. The subject may be asked to return to the clinic when necessary to have their asthma status evaluated.

Subjects who permanently discontinue IP will be requested to attend the Early Discontinuation of IP visit and will be strongly encouraged to complete any remaining study visits as per the Schedule of Activities (SoA; [Section 1.3](#)). Subjects who permanently discontinue IP and continue in the study will complete the Early Discontinuation of IP visit at the time of IP discontinuation and then return for the next visit in the Double-Blind, Placebo-Controlled visit sequence. At the visits subsequent to the Early Discontinuation of IP visit, study procedures will be completed except for dispensation/return of IP. Subjects who withdraw from the study, regardless of the reason, will be requested to return to the clinic to complete the Early Withdrawal (EW) from Study visit. All subjects who remain on IP through and including Visit 9 (Week 24) or who complete the EW from Study visit will be asked to return for a Follow-up visit approximately 4 weeks after their last dose of IP to assess subject safety.

Total duration for study participation per subject is up to 34 weeks (includes a Screening visit, followed by a 2-week to 6-week Run-in period to allow for collection of baseline eDiary data; a 24-week Double-Blind, Placebo-Controlled period; and 4-week Follow-up period).

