7. DISCONTINUATION OF INVESTIGATIONAL PRODUCT AND SUBJECT WITHDRAWAL FROM THE STUDY

7.1. Discontinuation of Investigational Product

Permanent discontinuation of IP does not mean withdrawal from the study, and remaining study procedures should be completed as indicated by the study protocol. If study IP is permanently discontinued, the subject will be encouraged to remain in the study and continue to complete all study visits as per the SoA ([Section 1.3](#)). If a subject permanently discontinues IP prior to Visit 8 (Week 20) and remains in the study through Visit 9 (Week 24), the subject will not need to return for the Follow-up visit.

[Sections 7.1.1](#) and [7.1.2](#) define mandatory criteria for permanent discontinuation of IP.

For subjects who simultaneously discontinue IP and withdraw from the study, the Early Discontinuation of IP visit procedures should be conducted, as shown in the SoA ([Section 1.3](#)), and a separate Early Withdrawal from Study visit is not needed. The subjects should be encouraged to return for the Follow-up visit.

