
 • Immediately discontinue IP • Report the event to the Medical Monitor within 24 hours • Complete the liver event eCRF and complete an SAE data collection tool if the event also met the criteria for an SAE^b • Perform liver chemistry follow-up assessments • Monitor the subject until liver chemistry test abnormalities resolve, stabilize, or return to baseline (see MONITORING) • Do not restart/rechallenge subject with IP unless Medical Monitor approval is granted • If restart/rechallenge not granted, permanently discontinue IP and continue subject in the study for any protocol specified follow up assessments 
MONITORING:
 
 • Repeat liver chemistry tests (include ALT, AST, GGT, alkaline phosphatase, total bile acids, bilirubin, and INR) and perform liver event follow-up assessments within 24 hours • Monitor subject twice weekly until liver chemistry test abnormalities resolve, stabilize, or return to baseline • A specialist or hepatology consultation is recommended 	
Additional Liver Panel
 
 • Viral hepatitis serology^d • Obtain INR and recheck with each liver chemistry assessment until the ALT and/or AST values show downward trend • Obtain blood sample for pharmacokinetic (PK) analysis • Serum creatine phosphokinase (CPK) and lactate dehydrogenase (LDH) • Fractionate bilirubin, if total bilirubin > 2x ULN • Obtain complete blood count with differential to assess eosinophilia • Record the appearance or worsening of clinical symptoms of liver injury, or hypersensitivity, on the adverse event (AE) report form • Record use of concomitant medications (including acetaminophen, herbal remedies, and other over-the-counter medications) on the concomitant medications eCRF • Record alcohol use on the liver event alcohol intake eCRF • Anti-nuclear antibody, anti-smooth muscle antibody, Type 1 anti-liver kidney microsomal antibodies, and quantitative total immunoglobulin G (IgG) or gamma globulins • Serum acetaminophen assay • Liver imaging (ultrasound, magnetic resonance, or computerized tomography) and/or liver biopsy to evaluate liver disease

^a Serum bilirubin fractionation should be performed if testing is available. If serum bilirubin fractionation is not immediately available, discontinue IP if ALT or AST \geq 3x ULN **and** bilirubin > 2x ULN. Additionally, if serum

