4.5. Safety Population

The safety population will include all subjects who receive at least 1 dose of study treatment, with subjects grouped according to their actual treatment. If GB001 was taken, subjects will be grouped according to the highest dose of GB001 actually taken (20 mg, 40 mg, or 60 mg) based on kit and study treatment accountability data. The safety population will be utilized for safety and PK analyses.

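### The by-visit GB001 concentration summaries have no on-treatment restriction, so samples drawn after a subject stops the drug can pull the by-dose means down, more at later visits

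*SAP*

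**What the plan says.** **Sampling after IP is stopped.** Protocol 7.1 says that after permanent discontinuation "the subject will be encouraged to remain in the study and continue to complete all study visits as per the SoA". Protocol 4.1.1 describes what happens at those visits: "At the visits subsequent to the Early Discontinuation of IP visit, study procedures will be completed except for dispensation/return of IP". For liver-related stops, Protocol Appendix 6 (Table 5) says: "If restart/rechallenge not granted, permanently discontinue IP and continue subject in the study for any protocol specified follow up assessments".

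**PK schedule.** As the extracted Schedule of Activities reads, PK samples are taken at Randomization (before and 2.5 hours after the dose), at Weeks 2, 12, 16, 20 and 24, and at the Early Discontinuation of IP and Early Withdrawal visits. Only the IP-dispensing row carries a note on subjects who have stopped IP. Protocol 8.5 does not make later samples conditional on recent dosing.

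**Analysis.** SAP 4.5 assigns PK to the safety population, that is, anyone with at least one dose. SAP 3.1 assigns visits by study day from first dose. SAP 8.3.3.4 states that "GB001 plasma concentrations will be summarized by visit/timepoint using the following descriptive statistics", and adds: "For calculation of mean concentrations, all below limit of quantification (BLQ) values will be set to zero". A by-subject listing is also planned.

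**The concern.** A by-dose, by-visit concentration table is normally read as exposure under treatment. Here, a subject who has stopped GB001 but still attends contributes a low or zero value to the mean for a dose no longer being taken. Stops accumulate, so the share of such values can only be expected to grow over the 24 weeks, and steady exposure on drug could then look like a decline.

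This is a question of which samples belong in the table, not of how BLQ is coded. Any BLQ convention would still mix the two kinds of sample. Apart from the listing, this table is the only PK output in the SAP, in a trial that lists plasma PK among its exploratory objectives.

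**Working it through.** The documents state no concentration or exposure figure, so there is nothing to reproduce first.

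**Step 1. Do off-drug samples arise?** The rule for post-discontinuation visits is that "study procedures will be completed except for dispensation/return of IP". PK sampling is not in that exception, and neither the Schedule of Activities nor Protocol 8.5 excludes it. So yes, for every subject who stops IP and still attends.

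**Step 2. Does the SAP remove them?**
- Population (SAP 4.5): at least one dose, so these subjects are in.
- Visit windows (SAP 3.1): based on study day, not dosing status. A scheduled Week 16 sample from a subject who stopped at Week 8 counts as Week 16.
- Summary (SAP 8.3.3.4): no condition on treatment status or time since last dose.

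Inclusion follows from these stated rules, although no sentence says so outright.

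**Step 3. Size at one visit.** Let f be the share of a visit's samples that are off drug and BLQ, hence zero. The reported mean is then (1 − f) × the on-drug mean. Counts assume all of the roughly 120 planned subjects per arm are sampled.

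| f (assumed) | Subjects of 120 | Reported / on-drug mean |
|---|---|---|
| 2% | 2.4 | 0.98 |
| 5% | 6 | 0.95 |
| 10% | 12 | 0.90 |
| 20% | 24 | 0.80 |

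Other statistics move too. With an assumed lognormal on-drug distribution and CV of 50%, f = 10% raises the CV to about 62%: √(0.90 × 1.25 − 0.90²) / 0.90 = 0.624. The median falls by about 6%.

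**Step 4. Pattern over time.** Assume IP stops accrue at a constant rate to a total F by Week 24, and that a fraction s of stoppers stay and are sampled. By week w the cumulative share stopped is c = 1 − (1 − F)^(w/24), and the ratio is (1 − c) / [(1 − c) + s·c].

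| F | s | Week 2 | Week 12 | Week 24 |
|---|---|---|---|---|
| 8% | 25% | 0.998 | 0.989 | 0.979 |
| 8% | 100% | 0.993 | 0.959 | 0.920 |
| 20% | 25% | 0.995 | 0.971 | 0.941 |
| 20% | 100% | 0.982 | 0.894 | 0.800 |

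For example, with F = 8% and s = 25% at Week 24: 0.92 / (0.92 + 0.02) = 0.979. F and s are both assumptions. The 8% in SAP 2.5 is a dropout rate, not a rate of stopping IP while staying in the study; it is used here only as a convenient low value.

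**Step 5. Are off-drug samples really BLQ?** Half-life and quantification limit are not given. With an assumed half-life of 72 hours, the fraction remaining is 0.5^(7×24/72) = 0.198 at 7 days and 0.5^(28×24/72) = 0.0016 at 28 days. BLQ is thus plausible by the next four-weekly visit, but not soon after the last dose. If off-drug samples average a fraction r of the on-drug mean, the ratio becomes 1 − f(1 − r), with f now the whole off-drug share. For f = 10% and r = 0.2 that is 0.92 instead of 0.90. The direction is unchanged, and Step 4 is an upper bound on the loss for its F and s.

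**The case against.** The best reply is that this infers a plan from silence. SAP 8.3.3.4 never mentions post-discontinuation samples. The Schedule of Activities and Protocol 8.5 describe later samples together with a recorded prior-evening dose, which a subject off IP cannot supply. The programmer might therefore exclude them. That is a fair reading of intent, but Protocol 4.1.1 points the other way and the SAP gives no rule to exclude on. The ambiguity itself needs closing.

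It is also fair that the size is unknown and may be near zero, that the table is descriptive and tertiary, that the median and the listing would show the zeros, and that Protocol 9.4.3 leaves room for a separate population PK analysis. All of this stands and limits the importance of the point. That separate analysis is optional, though, and would not correct the by-visit table.

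A reader might infer more than the documents support:
- **Highest-dose grouping (SAP 4.5).** It could seem to misfile samples. Dose modification is not permitted (Protocol 6.5) and kits are assigned by randomized group (Protocol 6.2.3), so the rule acts only through kit errors. Off-drug dilution would occur under any group label.
- **Liver-event samples.** Table 5 asks sites to "Obtain blood sample for pharmacokinetic (PK) analysis" once IP is stopped. Follow-up assessments are due within 24 hours, so such a sample may still be quantifiable. It is also unscheduled, and SAP 3.1 keeps only the evaluation closest to the target day in each window.
- **The 50% BLQ suppression rule.** It is out of reach at off-drug shares of 20% or less.

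**Conclusion.** The point holds in a limited form. Following the stated population, windowing and BLQ rules puts samples from subjects no longer taking GB001 into by-dose, by-visit means, and biases those means downward. The arithmetic mean falls by f. Under the scenarios above it is 0.98 to 1.00 of the on-drug mean at Week 2, 0.89 to 0.99 at Week 12 and 0.80 to 0.98 at Week 24. These ranges rest on assumed stopping rates (8% to 20%), assumed retention (25% to 100%) and off-drug samples being BLQ; the documents supply none of these.

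The consequence is a misleading descriptive PK table. No test or efficacy conclusion depends on it. It would be tempting to add that dose proportionality or the choice of dose is put at risk, but the documents do not support that. The SAP plans no dose-proportionality analysis. The exposure reasoning in Protocol 4.3 concerns earlier studies used to select doses for this trial. No dose decision is tied to this table.

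**What to change.** In SAP 8.3.3.4:
- Restrict the by-visit concentration summaries to scheduled samples taken on or before the IP stop date plus a short prespecified window after the last dose, and outside any recorded IP interruption. The sponsor should set the window from GB001's known elimination, which these documents do not give.
- Show post-discontinuation and unscheduled liver-event samples in the by-subject listing only, with time since last dose where available.

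The flag should rest on IP stop and interruption dates. Treatment duration is already needed for SAP 7.1 and 7.2. The evening dose times are less dependable as a basis: Protocol 8.5 puts them on a paper worksheet and does not say that they enter the database.

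The cost is one or two sentences, one programming flag and slightly fewer samples in the summary. Nothing is lost, because the excluded values remain in the listing.

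### Applied within one group, the SAP's PK display rule prints a measured maximum as BLQ, and a measured median too when fewer than half the values are BLQ

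*SAP*

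**What the plan says.** SAP section 8.3.3.4 contains three linked rules for GB001 plasma concentrations.

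- For the mean, "all below limit of quantification (BLQ) values will be set to zero".
- Once more than half of the results at a nominal timepoint are BLQ, "summary statistics for the timepoint will not be calculated".
- Where a summary is produced but its mean lies under the LLOQ, the instruction reads: "then the mean, median, minimum, and maximum concentration values will be set to BLQ".

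The listed statistics also include n, SD, arithmetic and geometric %CV and the geometric mean. None of these is named in the overwrite. On grouping, the section says only that "GB001 plasma concentrations will be summarized by visit/timepoint using the following descriptive statistics"; it does not mention treatment group. Section 4.5 assigns PK analyses to the safety population, which includes placebo subjects. Section 8.3.3.4 also states that "PK concentrations will also be presented in a by-subject data listing".

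**The concern.** The second rule removes timepoints where most values are BLQ. The third rule then treats what is left as if it were essentially all BLQ, on the evidence of the mean alone. A mean that contains zeros can fall below LLOQ while more than half the subjects have measured concentrations. In that case the table states that nothing was quantifiable, which is untrue. The row can also contradict itself: minimum and maximum both shown as BLQ beside an SD that may exceed the LLOQ. What is at stake is the accuracy of a summary table for an exploratory endpoint in a dose-ranging study. No test or estimate of efficacy or safety depends on it.

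**Working it through.** The documents give no LLOQ and no GB001 concentrations, and there is no plan figure to reproduce. The check is by logic, in units of LLOQ (LLOQ = 1). A BLQ value counts as 0 and every quantified value is at least 1. Let n be the number of observations in the group, b the number BLQ, and q = b/n. Assume that the 50% rule and the statistics use the same n observations. The trigger does not say which mean it refers to; the arithmetic mean is used here.

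1. **When the overwrite can act.** Summaries exist only if q ≤ 0.5, so at least half the values are quantified.
2. **Maximum.** At least one value is ≥ 1, so the maximum is ≥ 1. Showing it as BLQ is wrong whenever the overwrite acts. This step needs only the 50% rule, so it does not depend on which mean is meant.
3. **Minimum.** If every value were ≥ 1 the mean would be ≥ 1. A mean below 1 therefore needs at least one BLQ value, and the minimum is correctly BLQ.
4. **Median, q < 0.5.** The middle value (or both middle values) lies above the BLQ block, so the median is ≥ 1 and showing it as BLQ is wrong.
5. **Median, q = 0.5.** With BLQ counted as zero, the median is half the smallest quantified value. A mean below 1 requires the quantified values to average below 2, so the smallest is below 2 and the median is below 1. BLQ is then a fair display.

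**Enumeration.** All 12,869 data sets of size 1 to 8 on the grid {0, 1, 1.2, 1.5, 1.9, 2.5, 4, 8} were checked. The overwrite was triggered in 383. The maximum was quantified in 383 of 383 and the minimum was BLQ in 383 of 383. The median was ≥ 1 in 270; the other 383 − 270 = 113 all had exactly 50% BLQ. In 50,000 random lognormal data sets with n from 2 to 120, the overwrite was triggered 2,604 times, with the maximum quantified and the minimum BLQ in all 2,604. These counts confirm the logic; they say nothing about how often the rule would act in this trial.

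**Illustration (constructed values).** Take 45 BLQ values, 54 at 1.2 and one at 20, so n = 100 and q = 0.45.

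- Mean: (54 × 1.2 + 20)/100 = 84.8/100 = 0.848, below LLOQ.
- Median: the 50th and 51st ordered values are both 1.2.
- Maximum: 20.
- SD: √[(54 × 1.44 + 400 − 100 × 0.848²)/99] = √(405.85/99) ≈ 2.02; %CV = 2.02/0.848 ≈ 239%.

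The rule prints mean, median, minimum and maximum as BLQ, beside an SD of about twice the LLOQ.

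**How large a maximum can be overwritten.** With b = n/2, one value M and the remaining quantified values at 1, the mean is (n/2 − 1 + M)/n. This is below 1 when M < n/2 + 1. For n = 120 (the approximate group size in SAP section 2.4) that is M < 61 × LLOQ; for n = 20 it is M < 11 × LLOQ.

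**When the trigger is met.** The mean is below 1 only if the quantified values average less than 1/(1 − q): below 2 × LLOQ at q = 50%, 1.25 × at 20%, and 1.11 × at 10%.

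**The case against.** Four points can be made on the other side.

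- **Grouping.** A reader might infer that the BLQ maximum is false in every case, without condition. The SAP does not support that. Section 8.3.3.4 counts BLQ values per nominal timepoint and names no arm. If the 50% share were pooled over arms while statistics were shown by arm, placebo would supply about 120/480 = 25% of the observations, if its samples are assayed (the documents do not say). The timepoint need not be suppressed, the placebo mean would be 0, and a BLQ maximum would be right. The SAP neither describes nor excludes this combination, so the condition stands.
- **Frequency.** The trigger is narrow, as the last calculation shows. The Visit 2 predose sample should be almost all BLQ, because earlier GB001 participants are excluded (Protocol 5.2, criterion 13), and would be suppressed. The other samples are 2.5 hours postdose or at visits during evening dosing (Protocol 8.5). Against this, those later samples may be taken at any time during the visit, and the Schedule of Activities also has samples at early discontinuation and withdrawal, so a mix of BLQ and quantified values is conceivable. The documents do not settle how often it would occur.
- **What is hidden.** A reader might also infer that the highest exposures are lost or that dose-exposure conclusions are distorted. That goes too far. The listing holds the individual values, SD and %CV would still signal an outlying value, and nothing in the documents says that this table feeds the population PK analysis mentioned in Protocol 9.4.3.
- **Materiality.** Plasma PK is a tertiary/exploratory endpoint (Protocol section 3), and these summaries are descriptive. This is correct and keeps the point minor.

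None of this makes the overwritten maximum or median a true entry when the rule acts within one group.

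**Conclusion.** The rule is wrong as written, and the point is minor. It rests on one assumption, that the 50% rule and the statistics are applied to the same observations. It does not extend to the minimum, nor to the median at exactly 50% BLQ when the arithmetic mean is the trigger and BLQ counts as zero. The SAP states that substitution for the mean only; using it for the median is a further assumption. The number of affected timepoints cannot be derived from the documents and may be zero.

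**What to change.** Replace the overwrite sentence in SAP 8.3.3.4 with a rule applied statistic by statistic within the displayed group. The mean is shown as BLQ if it is below LLOQ; the median, minimum and maximum come from the observed values, and each is shown as BLQ only when it is itself below LLOQ. The same sentence should say that the 50% share is counted in that same group, which removes the ambiguity about pooling.

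Example: n = 120 with 48 BLQ (40%) and 72 values at 1.4 × LLOQ. The mean is 72 × 1.4/120 = 0.84 × LLOQ. The revised rule would show mean BLQ, median 1.4, minimum BLQ and maximum 1.4 (× LLOQ); the present rule shows all four as BLQ.

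The cost is one SAP sentence. Data collection, hypotheses and all other analyses are unchanged.
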